Monitoring and blunting coping tendencies have also been shown to influence the extent to which individuals prefer to pay close attention to their wellbeing or avoid thinking about it (Murris & Van Zuuren, 1992; Miller, 1987). Those who employ monitoring to cope with health problems will actively seek out health information, whereas those who employ blunting will adopt distraction strategies in order to actively avoid health information (Miller, 1995). This information seeking preference is important as evidence suggests that acquisition of health information can lead to increased health anxiety in individuals who exhibit monitoring coping preferences (Miller, 1995). In the case of menopausal symptom monitoring, women's attention is drawn to information about their menopausal wellbeing, which may be anxiety provoking. Therefore, this measure will help us understand whether symptom monitoring is more or less effective as an intervention for women, depending on their health information-seeking preferences.

It is important to establish for whom symptom monitoring might be most helpful, or conversely taxing or even harmful should it challenge a dispositional tendency to avoid focusing on wellbeing. Indeed, coping style and neuroticism have both been associated with increased health anxiety following the procurement of health information (Lagoe & Atkin, 2015; Miller, 1987). Therefore, health anxiety will also be measured during this research to explore whether symptom monitoring influences it, and whether this effect is related to neuroticism or coping preferences.

A third objective is to investigate whether participants attribute the act of monitoring to any perceived improvements, or whether participants attribute other elements of research participation to their improved health (i.e. increased menopausal awareness), or whether participants do not perceive any improvements whatsoever. Studies which have included symptom monitoring as a control intervention often speculate that involvement in research is responsible for the positive outcomes found in the control group, rather than symptom monitoring in itself (Borud et al., 2010). However, these studies rarely provide data on this assumption. Therefore, the present study aims to establish whether participation in menopausal research per se improves wellbeing, regardless of what that participation entails.

Summary of objectives:

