- Investigate whether daily symptom monitoring influences psychological, physical and behavioural health outcomes compared to a non-monitoring control group.
- Assess whether personality and coping style moderate the impact of symptom monitoring on physical or emotional health outcomes during the menopause.

[figure not shown]
FACULTY OF LIFE SCIENCES AND EDUCATION
FACULTY ETHICS SUB GROUP APPLICATION FORM

- Identify whether participants attribute any health improvements to symptom monitoring, or other elements of their research participation.

8. STATEMENT OF STUDY DESIGN (E.g. RCT, Crossover, Cohort studies, Case control, Action research, etc. Max 700 words)

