Both groups will complete a number of measures at baseline and at 2-week follow up, using surveys presented via JISC Online Surveys. Baseline measures will be: demographics, coping style, and trait neuroticism, as well as physical and emotional menopause symptoms (as measured using the DRK), health anxiety, help-seeking intentions, health and symptom awareness, willingness to engage in patient-doctor communication, and perceptions of efficacy in treatment decision-making and goal setting. Participants will be asked on the baseline questionnaire whether they would like to be sent text message reminders to help them remember to complete the surveys. Those who answer "Yes" will be asked to supply their mobile phone number. Participants will also be given the option of opting out of being sent text reminders throughout the duration of the study. This is in case participants find receiving daily text messages invasive, annoying, or not useful. Therefore, allowing participants to opt out gives them the option to change their

**FACULTY OF LIFE SCIENCES AND EDUCATION
FACULTY ETHICS SUB GROUP APPLICATION FORM**

mind. **See Appendix 1 to view the baseline survey in Word document format.** Prior to being presented with the information sheet, consent form, and baseline survey questions, participants will be asked three screening questions which will assess study eligibility. **See Appendix 2 to view the screening questions. The screening questions with the information sheet and consent form and main baseline survey questions, as presented on JISC Online Surveys, can be viewed via this link:** <https://southwales.onlinesurveys.ac.uk/baseline-questionnaire-preview>

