interested in receiving text message reminders, participants in the control group will also be sent a reminder text message to complete the follow-up survey.

Hypotheses:

- Symptom monitoring will lead to significant improvements in symptoms after 2 weeks, in comparison to the non-monitoring control group.
- The monitoring group will report increased self-efficacy at follow up in patient-doctor communication, shared decision making, goal orientated behaviour, help-seeking intentions, and heightened health awareness, compared to the control group.
- Women in the intervention group who are monitors according to their scores on the blunting and monitoring scale will report higher negative emotions and physical symptoms than blunters at follow up.
- Greater Health anxiety at follow up will be predicted by symptom changes, demographics (living alone, employment, and marital status), coping style, neuroticism, and symptom monitoring.

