Health anxiety subscale extracted from The Health Orientation Scale, $\alpha = .82$ (HOS; to be assessed at baseline and follow-up): health anxiety will be assessed to explore whether symptom monitoring influences it, and whether this effect is related to neuroticism or coping preferences. The HOS was developed by William E. Snell, and includes 10 health-oriented subscales each containing five items. The items on the health anxiety subscale assesses anxious feelings associated with the status of one's health. More specifically, these items were designed to tap people's feelings of tension, discomfort and anxiety about their physical health. People who endorse these items are those who experience chronic anxiety as a result of thinking about their physical health (Snell et al., 1991). The 5-item health anxiety subscale has good reliability, and has been used in numerous studies as a measure of health anxiety (Adejumo et al., 2017; Gordon et al., 2005; Snebby & Snell, 2002). **See Appendix 10, page 4 to view a copy of the original HOS including the Health Anxiety subscale, see Appendix 1, page 5 to view how the Health Anxiety subscale will be presented on the baseline survey. See Appendix 3, page 2 to see how to Health Anxiety subscale will be presented on the follow-up survey. On the baseline and follow-up surveys the health anxiety subscale is presented together with the health consciousness subscale and titled "Thoughts about health questionnaire".**

Patient-doctor communication will be assessed using the Willingness to Communicate about Health (WTCH) Measure, $\alpha = .70$: this variable will be explored following evidence from the systematic review which suggested that willingness to communicate about one's health might increase following symptom monitoring. This was because individuals felt better able to describe the totality of their symptoms after summarising them using a symptom monitoring instrument (Ismail et al., 2016; Woods et al., 2015).

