22. DATA ANALYSIS / STATISTICS

Please describe the arrangements for analysing your data (qualitative and quantitative). Where appropriate discuss what data/statistical analysis will be completed. Where used, please remember to discuss sample size and how the sample size was decided upon.

2 x 2 mixed between-within ANOVA:

The main analysis will include a 2x2 mixed between-within ANOVA to assess differences in symptoms among the symptom monitoring and control groups before and after the 2-week research period. The between-subjects component will encompass the differences in symptoms between the control and intervention groups; the within-subjects variable refers to differences in symptoms before and after the 2-week study period. It is expected that after 2 weeks of symptom monitoring the intervention group will exhibit a greater reduction in symptoms in comparison to the control group (i.e., a significant group x time interaction). As discussed, a power analysis was calculated to identify the minimum sample size needed to detect moderate effects, resulting in the decision to recruit 78 participants, with 39 participants being randomised into each group.

Regressions:

Multiple regressions will explore whether help-seeking intentions as continuous variables as predicted by symptom monitoring group (dummy coded), self-efficacy in patient-doctor communication, self-efficacy in shared decision making, health and symptom awareness, and self-efficacy in goal orientated behaviour, health anxiety, and menopausal symptom changes.

Logistic regressions will establish whether control or intervention group membership (as measured as a dichotomous “Invention/Control” variable) is predicted by health anxiety, variances in emotions and symptoms, help-seeking intentions, self-efficacy in patient-doctor communication, self-efficacy in shared decision making, health and symptom awareness, and self-efficacy in goal orientated behaviour.

Correlations:

FACULTY OF LIFE SCIENCES AND EDUCATION
FACULTY ETHICS SUB GROUP APPLICATION FORM

Correlations will also be computed to assess for associations between certain variables. For example, higher neuroticism X higher negative emotions.

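### Health anxiety is measured to see whether monitoring influences it, but section 22 never makes it an outcome, and hypothesis 4 lists post-allocation symptom change beside monitoring, so no stated analysis gives the effect of allocation

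*Combined protocol and SAP*

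**What the plan says.** Section 7 gives the reason for the measure: "health anxiety will also be measured during this research to explore whether symptom monitoring influences it". It follows a warning that women's "attention is drawn to information about their menopausal wellbeing, which may be anxiety provoking". Section 9 repeats the purpose under its outcome measures: "health anxiety will be assessed to explore whether symptom monitoring influences it, and whether this effect is related to neuroticism or coping preferences". The summary of objectives in section 7 is general: "Investigate whether daily symptom monitoring influences psychological, physical and behavioural health outcomes compared to a non-monitoring control group". Section 8 states that "Both groups will complete a number of measures at baseline and at 2-week follow up", and health anxiety is on both lists.

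Section 22 then gives four analyses:
- a mixed ANOVA, described for symptoms;
- multiple regression with help-seeking as outcome and health anxiety among the predictors;
- logistic regressions with arm as outcome and health anxiety among the predictors;
- correlations, with one example that involves neither arm nor health anxiety.

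Among the hypotheses in section 8, the second covers the between-arm differences on the other scales and omits health anxiety. The fourth is the only one with health anxiety as outcome: "Greater Health anxiety at follow up will be predicted by symptom changes, demographics (living alone, employment, and marital status), coping style, neuroticism, and symptom monitoring". The first reads: "Symptom monitoring will lead to significant improvements in symptoms after 2 weeks, in comparison to the non-monitoring control group".

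Section 10 removes from analysis anyone who does not complete all materials or comply fully. Sections 8 and 27 require 14 daily forms from the monitoring arm only.

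**The concern.** The question in sections 7 and 9 is causal: does being asked to monitor change health anxiety? Randomisation supports a direct answer, namely the arm difference at follow-up. No stated analysis delivers it. The one hypothesis with health anxiety as outcome names a variable that the plan itself expects allocation to change. With that variable in the model, the monitoring coefficient answers a different question: whether the arms differ among women with the same symptom change.

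Section 7 raises the possibility that monitoring provokes anxiety, and this is the scale chosen to look for it. If monitoring raised health anxiety wholly by making women report more symptoms, the conditional coefficient would average zero. If symptom relief offset a direct rise, the coefficient would be positive although allocated women were on average no more anxious.

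**Working it through.** **Inputs from the documents.** Section 10 gives an effect size of .40, two-tailed alpha .05, 26 completers per arm (52 in all) and 39 recruited per arm (78). No effect size, SD or correlation is given for health anxiety, so there is no figure of the plan's own to reproduce for this outcome. The general figure does reproduce: a noncentral F test with .40 read as Cohen's f gives power 0.807 at N = 52, and 52 / (1 - 0.33) = 77.6, rounded up to 78. For two equal groups, f = .40 corresponds to d = .80. Since the section labels .40 as d, symptom effects of .40 and .80 are both shown. The labelling is a separate matter.

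**Inputs assumed.** Within-arm SD 1; within-arm slope of health anxiety on symptom change 0.2, 0.4 or 0.6; baseline-to-follow-up correlation of health anxiety 0.6.

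**Step 1: joint or not.** The fourth hypothesis gives no order of entry. The closest guide is the help-seeking regression in section 22: "Multiple regressions will explore whether help-seeking intentions as continuous variables as predicted by symptom monitoring group (dummy coded", and the same predictor list ends with change in symptoms. Joint entry is therefore the natural reading, but it is borrowed from a model with a different outcome.

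**Step 2: size of the gap.** In least squares, with other predictors left aside,

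total effect - conditional effect = (within-arm slope) x (arm difference in symptom change).

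| Arm difference in symptom change | slope 0.2 | slope 0.4 | slope 0.6 |
|---|---|---|---|
| .20 | 0.04 | 0.08 | 0.12 |
| .40 | 0.08 | 0.16 | 0.24 |
| .80 | 0.16 | 0.32 | 0.48 |

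**Step 3: what this does to the answer.**
- Effect wholly through symptoms (+.40): total 0.08, 0.16, 0.24 SD; conditional 0.00.
- Exact offset (symptoms -.40, direct rise .40 x slope): total 0.00; conditional 0.08, 0.16, 0.24.
- Opposite signs are possible. With symptoms -.80, slope 0.5 and direct rise 0.2, total = 0.2 - 0.5 x 0.8 = -0.20; conditional = +0.20.
- An unmeasured cause shared by symptom change and anxiety (loading 0.4 on each) means the coefficient is not even the direct effect. With symptoms -.40, causal slope 0.5 and no direct effect, total = -0.20. The within-arm slope becomes 0.5 + 0.4 x 0.4 = 0.66, so conditional = -0.20 + 0.66 x 0.40 = 0.06.

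**Step 4: how often it would show.** In 20,000 simulated trials per setting, for the exact-offset case and fitted without baseline anxiety (which the fourth hypothesis does not list), the conditional coefficient was significant in 6.1%, 8.6% and 17.9% of trials at 26 per arm. At 39 per arm it was 6.5%, 11.6% and 24.9%. With no direct effect the rate was about 5% at every slope, so the test of the conditional effect keeps its level.

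**Step 5: the logistic regressions.** Arm is the outcome, so the result is log-odds of membership per unit of anxiety. With health anxiety alone the coefficient averages 0.00 when the total effect is zero. With symptom change also in the model, the exact-offset case at 26 per arm gives 0.10, 0.21 and 0.41 log-odds per SD. Neither form gives an arm difference in health anxiety.

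**Step 6: precision of the direct comparison.** With baseline adjustment the residual SD is sqrt(1 - 0.6 x 0.6) = 0.8. The 95% CI half-width is 2.01 x 0.8 x sqrt(2/26) = 0.45 SD at 26 per arm and 1.99 x 0.8 x sqrt(2/39) = 0.36 SD at 39. At 26 per arm an unadjusted t test has 80% power at 0.792 SD, so the adjusted model needs 0.792 x 0.8 = 0.63 SD (0.51 at 39).

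**The case against.** The fourth hypothesis is one sentence. It fixes no model, and entry in blocks or one predictor at a time would fit its wording. This stands, and it is why the point is conditional on joint entry. Under any other order, though, the plan still would not say which coefficient answers the question in sections 7 and 9.

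A reader might infer that the logistic analysis certainly conditions on symptoms. The documents do not support that: the regressions are in the plural, no time point is given, and the term for symptoms is loose. Single-predictor models are possible, and they would avoid the conditioning. They would still yield no difference on the scale of interest.

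The daily record form contains anxious emotions, and section 8 expects negative reactions to fall in the monitoring arm under the main ANOVA. An unadjusted arm comparison bearing on anxious mood therefore exists. This tempers the concern about harm, but the form is not the Health Anxiety subscale, and extending the ANOVA to that subscale would be an inference.

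The gap is also wider than health anxiety: section 22 names no plain arm comparison for the scales in the second hypothesis. That is true. Health anxiety differs in that the only hypothesis with it as outcome also names the post-allocation variable.

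Finally, an added arm comparison is not automatically protected by randomisation. Women made anxious by monitoring could stop returning forms and be removed under section 10, which can happen in one arm only. This stands and shapes the fix.

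**Conclusion.** The point holds in a limited form. Sections 7 and 9 ask whether monitoring influences health anxiety, and no stated analysis estimates that effect. If the fourth hypothesis is fitted with all its predictors together, its monitoring coefficient differs from the total effect by about 0.08 to 0.24 SD at a symptom effect of .40. Those sizes rest on assumed slopes. They are smaller than the 0.45 SD half-width of the direct comparison at 26 per arm, which itself assumes a baseline correlation of 0.6.

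A reader might infer an inflated false-positive rate. That is not supported. The rejection rates above 5% reflect a real direct effect, stay near nominal at slopes 0.2 and 0.4 with 26 per arm, and reach 18% only at slope 0.6 with exact cancellation, an extreme case. Nor do the documents say that the coefficient will be reported as the total effect. As a description of who is anxious, the model is legitimate. The defect is that nothing else is planned that could answer the question. The change should be made before analysis, but the outcome is secondary and the main symptom ANOVA is untouched.

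**What to change.** Add one named analysis to section 22: linear regression of follow-up Health Anxiety on arm and baseline Health Anxiety, with neuroticism, MBSS score and demographics as optional pre-allocation covariates, and without symptom change. Run it in all randomised women with follow-up data, however many daily forms they returned, so that the section 10 compliance exclusion does not apply to it. Report the arm difference with its 95% CI as the answer to the question in sections 7 and 9.

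Keep the fourth-hypothesis model as descriptive, and state that its monitoring coefficient is not the effect of allocation. Label arm-by-neuroticism and arm-by-MBSS terms exploratory.

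The cost is a paragraph and one more model on measures already planned, with no extra participants. Two limits remain. Precision is modest, so a null result would not rule out a moderate rise, and women lost before follow-up stay unaccounted for.

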9. MATERIALS AND METHODS

This study will use electronic means (online survey, email) and participants will receive a £20 Amazon voucher for completed participation. No face to face contact will occur between the research team and research participants. Participants will predominantly be recruited using JISC's online platform for connecting researchers with study participants (www.callforparticipants.com), as well as social media sites including Facebook and Instagram. Using these platforms, a research poster will be used to attract participants to the study and provide interested participants with a link to the screening questions, information sheet, consent form, and baseline survey. **See Appendix 7 to view the recruitment poster as it will be presented on www.callforparticipants.com, and shared on social media sites.**

The baseline survey (**see Appendix 1**) will collect the email addresses of interested participants. After submitting the baseline questionnaire, participants will be contacted via email with details about their group allocation and further instructions i.e. intervention participants will be instructed to complete 5-minute daily surveys each day for 14 days (see **Appendix 6, page 1** for instruction email template for intervention participants), whereas control group participants will be asked to continue as usual for 14 days (see **Appendix 6, page 2** for instruction email template for control participants). After the 14-day period both groups will be asked via email to complete the follow-up survey (**see Appendix 6, page 3**). The information sheet (**see Appendix 8**) and consent form (**see Appendix 9**) will precede the baseline survey and will provide full information about the nature of the study and details about what the participants in each group will be asked to do, including eligibility for the £20 incentive for taking part. The methodology for supplying participants with vouchers via email has been used in a previously approved study with no problems raised (ethics reference: 200401HR).

To avoid participants being burdened unnecessarily by reading information about a study for which they are not eligible (e.g., too young or not experiencing the menopause) participants will answer screening questions which will assess their age, the number of hot flushes they experience per day, and their self-reported menopausal status. Participants will be screened out of the survey if they indicate that they are under 18, or report fewer than 2 hot flushes per day, and do not self-report peri- or post-menopausal status. **See Appendix 1, page 1 to view how the screening questions will be presented on the baseline survey. See Appendix 2 to view the screening questions.**

NICE guidance recommends clinicians diagnose menopause (without the use of laboratory testing) based on whether a woman is not using hormonal contraception and has gone over 12 months without a period. NICE advises that perimenopause be diagnosed based on the presence of irregular periods and vasomotor symptoms, in women without a uterus perimenopause is diagnosed based on symptoms alone. Therefore, it was decided to use presence of vasomotor symptoms as criteria for assessing symptomatic menopausal status as this

FACULTY OF LIFE SCIENCES AND EDUCATION

FACULTY ETHICS SUB GROUP APPLICATION FORM

encompassed both symptomatic peri and postmenopausal women, as well as women who have undergone surgical menopause. Furthermore, numerous RCTs which have compared variances in symptom reports between intervention and control groups have used 2 hot flushes per day as a criterion for assessing menopausal symptomology and status, and for ensuring that groups are equal in terms of menopausal symptom burden (Carpenter et al., 2012; Otte et al., 2013; Fraser et al., 2005).

All questionnaires will be presented using the JISC online surveys platform: www.onlinesurveys.com. After completing the baseline questionnaire, and providing their email address, participants will be emailed within 24 hours of completion of the baseline survey with details of their group allocation and a unique username. See **Appendix 6, page 1** for the instruction email to intervention participants, and **Appendix 6, page 2** for the instruction email to control participants. Participants will be asked to confirm their username at the beginning of each subsequent survey they complete (i.e. the DRK or follow-up survey) and in any email contact with the researcher.

Materials:

Baseline measures:

Demographics and medical history (baseline only): Demographic variables to be measured are: age, town/country of residence, menopausal status, employment status, relationship status, living arrangements (i.e. are they living alone or with others?), date of last menstrual period, current medications being used (both for menopause and other conditions), and any current medical conditions. **See Appendix 1, page 2 to view how the demographic and medical history questions will be presented on the baseline survey.**

Blunting and monitoring coping preferences as measured using the Miller Behavioural Style Scale (MBSS; at baseline only): this will be used to assess dispositional monitor/blunter coping preferences, which might affect the extent to which women benefit from or feel uncomfortable with symptom monitoring. The MBSS asks the recipient to vividly imagine 4 different scenarios, and then choose how they would respond to each one from a list of statements. These statements give an indication of whether the respondent would react to the imagined situation by using a Monitoring or Blunting coping strategy. Three scores can be derived from the MBSS questionnaire. They are: (1) the total Monitoring score; (2) the total Blunting score; or (3) the total difference score- Monitoring minus Blunting. To create the total Monitoring and Blunting scores simply sum the Monitoring items (marked "M") and the number of Blunting items (marked "B") respectively. Once these individual scale scores are created, you can simply put them into the M-B equation to create the total difference score. **See Appendix 10, page 1 to view a copy of the original MBSS, see Appendix 1, page 13 to view how the MBSS will be presented on the baseline survey.**

Neuroticism as measured using the neuroticism scale (10 items; $\alpha = .86$) from the International Personality Item Pool scales (NEO-IPIP-10; baseline only): this measure was chosen because it has a high reliability statistic, is freely available to use, is based on Costa and McCrae's NEO Personality Inventory (NEO-PI-R) of which it is highly correlated ($\alpha = .82$), and has been used in numerous psychological articles, all of which are listed on the IPIP website (<https://ipip.ori.org/newPublications.htm>). The IPIP is a public domain collection of personality measures which are based on the 16PF Questionnaire and the Big Five personality traits. **See Appendix 10, page 3 to view a copy of the original NEO-IPIP-10, see Appendix 1, page 3 to view how the NEO-IPIP-10 will be presented on the baseline survey.**

Outcome measures:

Help-seeking intentions as assessed using The General Help Seeking Questionnaire (GHSQ; $\alpha = .85$): help-seeking intentions will be assessed because prior evidence suggests that symptom monitoring can lead to an increased intention to seek medical help (Shafran et al., 2019). Furthermore, difficulties in identifying and communicating symptoms can act as a barrier to help-seeking and findings from our systematic review suggest

**FACULTY OF LIFE SCIENCES AND EDUCATION
FACULTY ETHICS SUB GROUP APPLICATION FORM**

symptom monitoring may increase willingness to communicate with health providers (Salaheddin & Mason, 2016). Therefore, we endeavour to test whether help-seeking intentions can increase following symptom monitoring, as mediated by heightened willingness to communicate. The GHSQ has been designed to be adapted to the target population under assessment, therefore the following help-seeking source was added: "Internet sources including health websites, online forums (I.e. Mumsnet Quora Reddit), and social media accounts (I.e. Twitter, Instagram, Facebook)". "Parents" was removed as a help source, as the target population for this study might no longer be able to turn to their parents for help. Therefore "Other relative/ family member" was amended to: "Relative/ family member". **See Appendix 10, page 4 to view a copy of the original GHSQ, see Appendix 1, page 4 to view how the GHSQ will be presented on the baseline survey. See Appendix 3, page 1 to see how to GHSQ will be presented on the follow-up survey. On the baseline and follow-up surveys the GHSQ is titled "help-seeking questionnaire".**

Health anxiety subscale extracted from The Health Orientation Scale, $\alpha = .82$ (HOS; to be assessed at baseline and follow-up): health anxiety will be assessed to explore whether symptom monitoring influences it, and whether this effect is related to neuroticism or coping preferences. The HOS was developed by William E. Snell, and includes 10 health-oriented subscales each containing five items. The items on the health anxiety subscale assesses anxious feelings associated with the status of one's health. More specifically, these items were designed to tap people's feelings of tension, discomfort and anxiety about their physical health. People who endorse these items are those who experience chronic anxiety as a result of thinking about their physical health (Snell et al., 1991). The 5-item health anxiety subscale has good reliability, and has been used in numerous studies as a measure of health anxiety (Adejumo et al., 2017; Gordon et al., 2005; Snebby & Snell, 2002). **See Appendix 10, page 4 to view a copy of the original HOS including the Health Anxiety subscale, see Appendix 1, page 5 to view how the Health Anxiety subscale will be presented on the baseline survey. See Appendix 3, page 2 to see how to Health Anxiety subscale will be presented on the follow-up survey. On the baseline and follow-up surveys the health anxiety subscale is presented together with the health consciousness subscale and titled "Thoughts about health questionnaire".**

Patient-doctor communication will be assessed using the Willingness to Communicate about Health (WTCH) Measure, $\alpha = .70$: this variable will be explored following evidence from the systematic review which suggested that willingness to communicate about one's health might increase following symptom monitoring. This was because individuals felt better able to describe the totality of their symptoms after summarising them using a symptom monitoring instrument (Ismail et al., 2016; Woods et al., 2015).

The 10-item WTCH measure uses a 5-point Likert scale which asks the responder to indicate how strongly they agree with each statement. These statements aim to capture how comfortable the respondent feels discussing their health and symptoms with others. The WTCH was chosen for this study because it has been found to have good reliability ($\alpha = .70$) as well as convergent and discriminant validity (Wright et al., 2007). **See Appendix 10, page 6 to view a copy of the original WTCH, see Appendix 1, page 7 to view how the WTCH will be presented on the baseline survey. See Appendix 3, page 4 to see how to WTCH will be presented on the follow-up survey. On the baseline and follow-up surveys the WTCH is titled "health communication scale".**

Decision-making efficacy will be assessed using The Decision Self-Efficacy (DSE) Scale, $\alpha = 0.85$: This variable will be explored following evidence from the systematic review which suggested that symptom monitoring is related to improved efficacy in medical decision making. This measure includes 11 items which assess self-confidence or belief in one's abilities in decision making, including shared decision making, in medical contexts. This instrument has been used in numerous studies which have explored whether certain health interventions have led to improvements in decision self-efficacy within health contexts (Minneci et al., 2019; Smith et al., 2019; Cuypers et al., 2018). Furthermore, this measure has been found to have good scale reliability ($\alpha = 0.85$; Cuypers et al., 2018). **See Appendix 10, page 8 to view a copy of the original DSE, see Appendix 1, page 8 to view how the DSE will be presented on the baseline survey. See Appendix 3, page 5 to see how to DSE will be presented on the follow-up survey. On the baseline and follow-up surveys the Decision-making self-efficacy scale is titled the "decision making scale".**

FACULTY OF LIFE SCIENCES AND EDUCATION
FACULTY ETHICS SUB GROUP APPLICATION FORM

Goal setting efficacy will be assessed using the General Self Efficacy Scale (GSE, $\alpha = 0.76$ to 0.90): This variable will be explored following evidence from the systematic review which found that symptom monitoring may improve an individual's ability to identify which health improvements they would like to see in the future. The GSE is a 10-item scale with a score for each question ranging from 1 to 4. The scale was created to assess a general sense of perceived self-efficacy. The construct of perceived self-efficacy reflects an optimistic self-belief that one can perform novel or difficult tasks, or cope with adversity in various domains of human functioning (Schwarzer, 1992). The 10 items on the GSE are designed to tap into the construct of perceived self-efficacy which has been positively related to goal-setting and health-related behavioural changes (Schwarzer, & Fuchs, 1996; Schwarzer & Jerusalem, 1995). Furthermore, several studies have shown that the GSE has high reliability, stability, and construct validity. **See Appendix 10, page 10 to view a copy of the original GSE, see Appendix 1, page 9 to view how the GSE will be presented on the baseline survey. See Appendix 3, page 6 to see how to GSE will be presented on the follow-up survey. On the baseline and follow-up surveys the GSW is titled the “self-efficacy scale”.**

Health awareness was assessed using the Health Consciousness subscale extracted from The Health Orientation Scale (HOS, $\alpha = 0.82$): This variable will be explored following evidence from the systematic review which suggested that symptom monitoring could increase health awareness. The items on the Health Consciousness subscale refer to an awareness of one's health. These items were designed to measure people's tendency to think about and to reflect about their health. People who endorse these items are those who think about that status of their physical health, and who in general are reflective about the nature of the health and wellness of their body (Snell et al., 1991). This measure was chosen for its simplicity, high reliability coefficient ($\alpha = 0.82$) and because it has been employed in a number of studies (Adejumo et al., 2017; Gordon et al., 2005; Sneyby & Snell, 2002). **See Appendix 10, page 5 to view a copy of the original HOS including the Health Consciousness subscale, see Appendix 1, page 5 to view how the Health Consciousness subscale will be presented on the baseline survey. See Appendix 3, page 2 to see how to Health Consciousness subscale will be presented on the follow-up survey. On the baseline and follow-up surveys the health consciousness subscale is presented together with the health anxiety subscale and titled “Thoughts about health questionnaire”.**

The Daily record keeping form (DRK): participants in both groups will complete the DRK at baseline and at follow-up. Only the intervention group will complete the DRK every day of the 2-week period.

An RCT conducted by Lancastle compared outcomes of implementing a positive reappraisal coping intervention, with a positive mood induction control, and a daily monitoring control as measured using the DRK (Lancastle, 2006). This study evaluated emotional reactions and physical symptoms among women experiencing 14-day IVF waiting periods. This research found significant improvements in physical symptoms within the daily monitoring group across the 2-week waiting period which suggests that 2 weeks is an adequate amount of time to generate observable effects of an intervention, using daily symptom monitoring.

For the present study, the DRK will be amended to include a comprehensive list of 32 menopausal symptoms, as indexed by the British Menopause Society (2016), as well as emotional reactions. The original DRK was developed to measure emotional distress of women undergoing IVF waiting periods, thus valid and statistically reliable facets of the DRK have been shown to effectively track changes in emotions related to depression, anxiety, anger, uncertainty, and positive affect (Boivin, 1997). Whilst the majority of these emotions are highly relevant to midlife women, the present study also includes emotions associated with loneliness. This is because feelings of loneliness have frequently been reported among menopausal women (Bingol et al., 2019). The menopause is considered by some to be a taboo subject, leading many to undertake the burden of their symptoms alone; this stoic resolve can make many women feel isolated and disconnected from friends, family members, and their partners. Research has explored the influence loneliness has on menopausal symptoms, and these studies have reported strong, negative associations, suggesting that loneliness can worsen the felt experience of physical symptoms (Thurston et al., 2008; Fernández et al., 2012; Hu et al., 2017; Bingol et al., 2019).

FACULTY OF LIFE SCIENCES AND EDUCATION
FACULTY ETHICS SUB GROUP APPLICATION FORM

Therefore, the present study will include items from previously validated measures of loneliness. The following emotional facets of loneliness will be included on the DRK: Isolated (as included in the UCLA loneliness scale), Rejected (as included in the De Jong Gierveld Scale), Lonely (as included in the direct measure of loneliness), Left out (as included UCLA loneliness scale). Cronbach's analyses will be conducted on these emotional facets to evaluate their reliability as a brief, daily, measure of loneliness.

